2.1. Primary aim

To determine safety, tolerability, and efficacy of integrating OXT dosing within a CBI-SST curriculum for social cognitive impairments in ASD. Eighty youth, ages 8-11 with ASD will be randomized into 1) Integrated Oxytocin and NETT- ASD(ION-ASD) or 2) control condition (facilitated play group) to evaluate: (A) safety and tolerability of targeted, intra-nasal OXT dosing within a 12-session, CBI-SST group curriculum, and (B) group differences on dual domains associated with social learning: social behavior and social cognition. Our working hypothesis, supported by pilot data, is that ION-ASD will be associated with greater differential improvement on dual targets of social behavior and social cognition relative to the control condition.

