- **Electrocardiogram.** Trained staff will collect EKG on each subject and this will be read & confirmed by a pediatric cardiologist at screening/baseline for all participants and week 12 (optional for participants in social play condition, i.e. non-medication arm).
- **Safety Labs** (to the extent possible, blood samples will be obtained at approximately the same time of day and under non-fasting conditions). Blood monitoring will occur at screening/baseline and week 12 for safety purposes, and the time between safety labs and the start of the study medication must be not more than 30 days. Total blood collected is 8.5 ML in SST tube at each time point –screening and week 12. screening for all participants and week 12 (optional for participants in social play condition, i.e. non-medication arm).
 - Chemistry Panel: The chemistry panel will include glucose (random, non-fasting), CO2, CL, K, Na, Creatinine, BUN, Mg
 - Routine Hematology
 - Liver Profile: AST, ALT
 - Urinalysis

Confidential

Rush University Medical Center

- Pregnancy test: All menstruating female participants will have a urine pregnancy test completed at screening and week 12 but the pregnancy test can be done at any time throughout the course of the study at the physician's discretion. In case of a positive pregnancy test, the participant will be dropped from the study and referred appropriately.

Routine hematology and blood chemistry and urinalysis will be done before final baseline visit. Due to the nature of ASD, it may be difficult to complete routine hematology and blood chemistry, liver profile and urinalysis at screening. Therefore, these tests can be done during the screening or baseline visit. Participants will not be randomized prior to the treating clinician reviewing and signing off on all results.

- *Diagnostic evaluation.*

- *Autism Diagnostic Interview, Revised (ADI-R):* The ADI-R is a semi-structured, investigator-based interview for caregivers of children and adults for whom autism or pervasive developmental disorders is a possible diagnosis.. The detailed interview focuses on early development in social and communication and self-help skills of the child, and takes approximately 2 hours to administer. The ADI-R will be allowed to be administered virtually via a HIPAA complaint platform (i.e. Zoom) if needed to reduce in person interaction between clinician and participant caregiver.

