4.3. Safety Assessments

Adverse events will be systematically reviewed by study clinician and each study will have a back-up physician to assess safety. The study clinician will also do a general inquiry about health, other medications, and visits to medical care providers since the last visit. The following safety measures will be completed either in-person or may take place virtually via a HIPAA compliant platform (i.e. Zoom) if needed to reduce the amount of in person interaction between study team and participant.

- *Clinical Global Impressions – Improvement Scale – Global (CGI-I)*. The CGI-I employs a seven point (1 = very much improved to 7 = very much worse) to determine the patient's improvement in response to treatment. The CGI-I has been successfully used as an outcome measure in previous psychopharmacology trials including the RUPP trial of risperidone in children with ASD, and the STAART funded citalopram trial. The rating convention for assigning CGI scores is to use all available data including direct observation, scales, and patient report to inform clinical judgment. CGI-I, Global will be used to evaluate safety, with the requirement that individuals scoring CGI of 6 or greater for 2 or more weeks be discontinued from the study and provided with appropriate referrals.
- *Adverse event rating form*
This is a semi-structured interview that has been modified to assess OXT specific side effects for a recently completed pediatric trial of sustained oxytocin treatment in ASD ⁵². It contains a general inquiry, drug-specific queries, as well as several questions about daily activities (e.g., sleep, appetite, energy level, bowel and bladder function). This instrument has been widely used in other autism related clinical trials. In addition to these measures, vital signs (heart rate, blood pressure) will be measured biweekly at the following visits: screening, baseline/week 1, week 3, week 5, week 7, week 9, week 11, week 12, week 16, and week 24 (or another biweekly schedule depending on start days/dates) Standardized procedures will be used for all physical measurements. We will attempt to do vital signs following a 4 minute period of rest, with the participant seated. Height and Weight will be taken at screening, baseline, Week 12, and Week 24 with all outer wear and shoes removed at every visit.

5. Study Treatment

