Caregiver reports on the ABC, PDDBI-SV, Griffith Empathy Scale, Children's Communication Checklist, CASI-5, Caregiver Strain, Vineland 3, SRS-2, RBS-R, and AIM will be collected at midpoint along with CGI-I ratings (blinded). Ratings may be conducted +/- 7 days from week 6 group depending on family schedules.

Week 12 (Endpoint)

The end of treatment visits occurs at Week 12 (to take place within \pm 7 days from the target date). At these visits, blood work, vital signs, temperature, height, weight, and an ECG will be completed. In addition, participants will undergo a series of assessments, which are anticipated to take approximately 4-6 hours to complete. The visit can be split into as many as three visits if this is better for the participant. The following measures will be completed: the CGI-I (Global and Social), the AE rating form, the Bates & Reilly Conversational Task, the CY-BOCS, Let's Face It, the RMET, the CASI-5, the RBS-R, the SRS, the ABC, the BFRT, the BASC-3, the PDDBI-SV, the Griffith Empathy Scale, the CCC, the Caregiver Strain, the DANVA2, the TAT, , and the GEMEP emotion recognition test, and sensor-based social-communication monitoring tests.

Week 16 & Week 24 (Maintenance visits 1 & 2)

There will be an additional follow-up appointment 12 weeks (\pm 7 days) after the participant stops taking the study drug. This visit is primarily to examine safety of OXT discontinuation, and look for possible maintenance of any favorable effects of ION-, and longer term safety. The assessments completed during this visit are identical to the Week 12/end of treatment visit.

Termination Visit: A participant may voluntarily withdraw from the study at any time. The PI has the right to discontinue a subject from this study or withdraws a participant from the study at any time. Every effort will be made to obtain information on subjects who withdraw. Participants who discontinue study drug prematurely will be asked to return to the clinic and complete all end of study safety lab work (week 12 blood work).

Participants will also be asked to complete all endpoint study procedures on their final visit before withdrawal to allow for true intent to treat analysis.

Missed Visits and Visit Windows

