- Mild*: events require minimal or no treatment and do not interfere with the subject's daily activities.
- Moderate*: events result in a low level of inconvenience or concern with the therapeutic measures. Moderate events may cause some interference with functioning.
- Severe*: events interrupt a subject's usual daily activity and may require systemic drug therapy or other treatment. Severe events are usually incapacitating.
- Life-threatening*: Substantial risk dying or requires intervention to prevent death.
- Death related to AE*: Subject died as a result of the event, self-explanatory.

Changes in the severity of an AE will be documented to allow an assessment of the duration of the event at each level of intensity to be performed. Adverse events characterized as intermittent require documentation of onset and duration of each episode.

Relationship to Study Treatment. Study clinicians will assess and document whether the AE is related to treatment condition. However, the relationship to study treatment will not be a factor in determining whether or not an AE is reported in this study. If there is any doubt as to whether a clinical observation is an AE, the event will be reported. All AEs must have their relationship to study product assessed using the terms: associated or not associated. In a clinical trial, the study product must always be suspect. To help assess, the following guidelines are used.

- Certain*: The adverse event and administration of the study drug are related in time, and a direct association can be demonstrated.
- Probably*: The adverse event and administration of the study drug are reasonably related in time, and the adverse event is more likely explained by the study drug than other causes.
- Possible*: The adverse event and administration of the study drug are reasonably related in time, and the adverse event can be explained equally well by causes other than the study drug.

Confidential

Rush University Medical Center

- *Unrelated*: The adverse event is clearly explained by another cause not related to the study drug.
- *Unknown or not applicable*

Reporting Procedures: Serious Adverse Events & Unanticipated Problems

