8.8. Statistical analysis

Specific Aim 1 & Exploratory Aim 1: Safety and tolerability will be analyzed by analyzing for group differences on total scores and domains of the AE form and satisfaction surveys respectively. Efficacy analysis will be follow analytic procedures used to derive social behavior and social cognition composites for the Seaver-NETT RCT¹⁶. First, a principal components analysis with varimax (orthogonal) rotation will be conducted on subscales of the primary social behavior measures - Griffith Empathy Scale and CCC-2; and raw total scores on primary social cognition outcomes – RMET and DANVA2. The PCA is used to develop composite scores in a field with no viable outcomes for higher-order core social impairments as well as to minimize floor and ceiling artifacts, effects of variability in response, and other sources of measurement error. Variables with high factor loadings for subscales will be entered into composite score development for the social cognition and social behavior composites. Missing, invalid, and/or incomplete data (i.e. more than 30% items missing when not pre-defined by scale) will be excluded from the factor analysis.

A linear mixed model analysis will be conducted on all participants with at least two of four available time points (Wk 0, Wk 12, 1-mon, 3-mo). Composite scores of co-primary outcomes social behavior and social cognition will be used as the response variable; treatment condition, time, and condition * time interactions will be covariates. Verbal IQ will also be entered into the model in exploratory moderator analyses. We will estimate effect sizes (Cohen's d) and confidence intervals (95%) acknowledging the likelihood that analyses may not permit definitive conclusions given the likely size of the confidence intervals.

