| | Scrn (1-2) | Scn/ BL (1-2) | WK1 | WK2 | WK3 | WK4 | WK5 | WK6 | WK7 | WK8 | WK9 | WK10 | WK11 | WK12 | WK16 | Wk24 |
|--|---------------|---------------------|-----|-----|-----|-----|-----|-----|-----|-----|-----|------|------|------|------|------|
| Parent Questionnaires | | | | | | | | | | | | | | | | |
| ABC | X | | | | | | | X | | | | | | X | X | X |
| PDDBI-SV | | X | | | | | | X | | | | | | X | X | X |
| Griffith Empathy Scale | | X | | | | | | X | | | | | | X | X | X |
| Children's Communication Checklist | | X | | | | | | X | | | | | | X | X | X |
| CASI-5 | | X | | | | | | X | | | | | | X | X | X |
| Caregiver Strain | | X | | | | | | X | | | | | | X | X | X |
| Vineland 3 (Survey Form) | | X | | | | | | | | | | | | X | | X |
| SRS-2 | | X | | | | | | X | | | | | | X | X | X |
| RBS-R | | X | | | | | | X | | | | | | X | X | X |
| Autism Impact Measure | | X | | | | | | X | | | | | | X | X | X |
| Parent expectancy questionnaire | | X | | | | | | | | | | | | X | X | X |
| SSIS | | X | | | | | | | | | | | | X | X | X |
| Participant Assessments | | | | | | | | | | | | | | | | |
| Strange Stories Test | X | | | | | | | | | | | | | | | |
| Reading Mind in Eyes Test ¹ | | X | | | | | | | | | | | | X | X | X |
| DANVA2 ¹ | | X | | | | | | | | | | | | X | X | X |
| TAT ¹ | | X | | | | | | | | | | | | X | X | X |
| Biological motion task ¹ | | X | | | | | | | | | | | | X | X | X |
| AEDEA | | X | | | | | | | | | | | | X | X | X |
| Medication | | | | | | | | | | | | | | | | |
| Dosing Instructions | | | X | | X | | X | | X | | X | | X | | | |
| Medication Dispensing Log (staff) | | | X | | X | | X | | X | | X | | X | | | |
| Medication Compliance | | | X | | X | | X | | X | | X | | X | X | X | |
| Medication Diary Dispensed | | | X | X | X | X | X | X | X | X | X | X | X | | | |

Confidential

Rush University Medical Center

WORKS CITED

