Official title: Integrated Oxytocin and Nonverbal, Emotion Recognition, and Theory of Mind

Training for Children With Autism Spectrum Disorder

NCT number: NCT02918864

Document date: 2/8/2021

Statistical Analysis Plan

Data Reduction and Outcome Variables. Safety and tolerability will be evaluated by comparing group differences on total counts and domains of the AE form and ratings on parent satisfaction surveys respectively. Efficacy analysis will follow analytic procedures used to derive social behavior impairment (SBI) and social cognition (SC) composites for the Seaver-NETT RCT16. First, principal components analysis (PCA) with promax rotation will be conducted on the primary social behavior impairment measures, the Nonverbal Communication and Social Relations subscales of the Children's Communication Checklist-2 (CCC-2) and the total score of the Griffith Empathy Scale (GEM). A separate PCA will be conducted on the primary social cognition outcomes, the Reading the Mind in the Eyes Test (RMET) and Diagnostic Analysis of Nonverbal Accuracy-2 (DANVA-2). The PCAs are used to confirm that these measures contribute to previously identified constructs in a field with no viable outcomes for higher-order core social impairments as well as to minimize floor and ceiling artifacts, effects of variability in response, and other sources of measurement error.

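### Oxytocin tolerability, part of primary aim 1(A), is assigned to an arm difference in parent satisfaction, and no planned analysis reports how many children stopped the drug because of an adverse event

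*Protocol*

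**What the plan says.** Protocol 2.1 sets as part (A) of the primary aim the evaluation of "safety and tolerability of targeted, intra-nasal OXT dosing within a 12-session, CBI-SST group curriculum". Protocol 8.8 gives the analysis: "Safety and tolerability will be analyzed by analyzing for group differences on total scores and domains of the AE form and satisfaction surveys respectively". The SAP, under Data Reduction and Outcome Variables, repeats it as a comparison of arms on "total counts and domains of the AE form and ratings on parent satisfaction surveys respectively". Both documents pair the terms in order, so the AE form serves safety and the satisfaction surveys serve tolerability. Protocol 8.2 adds only that the safety analysis concentrates on treatment-emergent events.

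The comparator is facilitated play (Protocol 5.1). Protocol 4.1 makes the week 12 ECG and laboratory tests "optional for participants in social play condition, i.e. non-medication arm". No placebo spray is planned for controls.

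The protocol foresees children coming off the drug. Sections 3.7 and 8.5 allow withdrawal for adverse events, and 5.2 says: "Participants who discontinue study drug prematurely will be asked to return to the clinic and complete all end of study safety lab work". It also collects relevant data: an AE interview "modified to assess OXT specific side effects" (4.3), severity grades and drug relatedness (8.5), and a dose diary with room for comments plus bottle weights (5.3).

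**The concern.** Whether a child can tolerate a drug is usually judged by side effects and by whether the child has to stop because of them. The plan gives the word tolerability to a different quantity: how much more or less satisfied parents are in one arm than in the other. The arms differ in two ways at once, the therapy programme and the drug. A question about the spray has no counterpart in the control arm, and general satisfaction mixes the two components.

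A report that follows the written rule would present satisfaction with a package, relative to a play group, as tolerability of oxytocin. The number of children who could not continue the drug because of an adverse event would have no defined place in the results. That matters here because Protocol 8.9 concedes the trial may be underpowered and justifies it partly by the tolerability information it will give. A follow-on trial of the combined treatment would want that number.

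**Working it through.** **Step 1: what each planned or collected item can show about stopping the drug.**

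| Item | Where | What it gives | AE-related stops reported? |
|---|---|---|---|
| Satisfaction ratings by arm | Protocol 8.8; SAP | Package versus play, drug and programme combined | No |
| AE-form totals and domains by arm | Protocol 8.8; SAP | How often side effects occur | No |
| Focus on treatment-emergent events | Protocol 8.2 | Which events count | No |
| AE data items | Protocol 8.1, 8.5 | Description, severity, relatedness; action taken with the drug is not listed | No |
| Withdrawal and stopping rules | Protocol 3.7, 8.5 | Conduct rules | Not summarised |
| Termination visit | Protocol 5.2 | Safety laboratory work and endpoint procedures | Not summarised |
| Dose diary and bottle weights | Protocol 5.3 | Drug use; no reason code specified | Not in 8.8, 8.9 or the SAP |
| Safety board review of drop-outs | Protocol 8.6 | Oversight, not specific to the drug or to AEs | Not a planned analysis |

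The remaining analysis text (Protocol 8.9 and the rest of the SAP) covers efficacy, predictors and responders, and adds nothing on tolerability.

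**Step 2: the plan's own figure.** There is none. Neither document gives an expected rate, margin or precision for tolerability. The power statement in 8.9 concerns a difference in means.

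**Step 3: what a direct count would deliver.** The size of the oxytocin arm is taken as a range, because the documents give different totals with 1:1 allocation:
- 25, stated per group in 8.9
- 70/2 = 35, from Phase 2 in 3.1
- 80/2 = 40, from 2.1
- 90/2 = 45, from 3.5

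With no events, the upper limit of the exact two-sided 95% interval is 1 − 0.025^(1/n). The chance of seeing at least one stop when the true rate is p is 1 − (1 − p)^n. The documents give no value for p, so 2%, 5% and 10% are assumptions.

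| n in oxytocin arm | Upper limit, 0 stops | At least one stop, p = 2% | p = 5% | p = 10% |
|---|---|---|---|---|
| 25 | 13.7% | 39.7% | 72.3% | 92.8% |
| 35 | 10.0% | 50.7% | 83.4% | 97.5% |
| 40 | 8.8% | 55.4% | 87.1% | 98.5% |
| 45 | 7.9% | 59.7% | 90.1% | 99.1% |

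Worked example for n = 25: 1 − 0.025^(1/25) = 1 − 0.863 = 13.7%, and 1 − 0.95^25 = 72.3%. With three stops in 35 children, the estimate is 3/35 = 8.6% and the exact interval runs from 1.8% to 23.1%.

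**The case against.** The strongest reply is that the trial tests a package. Aim 1(A) concerns dosing inside a skills curriculum, and Protocol 2.3 hopes for a treatment that is socially valid as well as safe. Parent satisfaction suits that purpose, and being unable to separate drug from programme is a feature of every between-arm comparison in this design. This stands as a reason to keep the survey as an acceptability measure. It does not make the survey a measure of drug tolerability, which can be described within the oxytocin arm without a comparator.

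A second reply is that too much rests on one word, and that AE-form results are tolerability evidence under either label. Much of this stands. The form asks about drug-specific effects and daily functions, severity grading reflects interference with activities, and 8.5 requires that "All AEs must have their relationship to study product assessed using the terms: associated or not associated". A reader might infer that tolerability goes unassessed; the documents do not support that. However the sentence is read, though, totals and domains show how often events occur and not who had to stop.

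A third reply is that stops could be tabulated from records already kept. That is true, and it makes the remedy cheap. But a table that could be produced is not one the plan commits to.

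A reader might also infer that the satisfaction survey does not exist, since no readable assessment list or schedule row names it and the nearest row in Appendix A is "Parent expectancy questionnaire". That goes too far. Figure 3, on weekly procedures, is not shown, and the lists are incomplete elsewhere: GEMEP is in the visit text but not in the readable schedule, and the SSIS is in the schedule but not in the visit text.

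**Conclusion.** The point holds in a limited form. Both documents assign tolerability to an arm difference in satisfaction, that difference cannot isolate oxytocin, and no planned analysis reports AE-related discontinuation of the drug. Side-effect frequency will still be reported, and no efficacy conclusion is affected. The plan should be corrected, but the gap does not undermine the trial.

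The conclusion rests on reading the pairing as written, on the control arm receiving no spray, and on the readable text of both documents. It does not depend on the assumed stop rates, which serve only to show precision.

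Two stronger inferences are not supported. One is a numerical claim about how far satisfaction would mask intolerance: the documents give no survey scale, spread or expected difference, so no size can be put on it. The other is that a direct count would settle whether oxytocin is tolerated. Seeing at least one stop is not an inference about the rate, and it should not be set against the power of a significance test. At a true rate of 2% the chance of seeing any stop is only 40% to 60% across the possible arm sizes; at 5% it is 72% to 90%, and at 10% it is 93% to 99%. The 5% attrition in 8.9 is study attrition and does not supply a rate for drug stops. The count is worth having because it measures the right thing, even though its interval will be wide.

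**What to change.** In Protocol 8.8 and the SAP:

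1. Define drug tolerability as the number and proportion of ION-ASD children, among those with at least one dose, who permanently discontinue oxytocin because of an AE by week 12. Give an exact (Clopper-Pearson) 95% interval. Take the events from the existing withdrawal, AE and diary records.
2. Report AE-related interruptions separately against a stated threshold, for example all doses in a week withheld. Without a threshold, one dose skipped for nasal irritation would count the same as stopping for good.
3. Present both alongside the AE-form comparison, which stays as planned.
4. Relabel satisfaction as programme acceptability.

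The cost is a protocol and SAP amendment, one analysis paragraph, and a review of existing records. No visits or participants are added. A new reason code in the diary could help, but it should not be the main source: the SAP, dated February 2021, describes some scoring in the past tense, so children may already have been treated and a new field would miss them. The downside is that the result is uncontrolled, descriptive and imprecise, and depends on open-label attribution of the reason for stopping. The report should say so.
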